The proposed project builds directly on the work of an earlier NIAAA-funded project (R21AA17596; [name], PI (Ojibwe, MPI on this project)). Using intensive community-based participatory research (CBPR) methods, 25,26 tribal community and AEP prevention experts guided the adaptation of CHOICES (Changing High-risk alcohOl use and Increasing Contraception Effectiveness Study),²⁷ an evidence-based brief AEP intervention supported by the CDC, for use with young American Indian women age 16-20. CHOICES relies on motivational interviewing (MI) to increase contraceptive use and decrease drinking among adult women at risk for an AEP. 27 The adapted version, American Indian Youth CHOICES (AIY-C) preserves the brief MI format and focus on AEP prevention through increased contraceptive use and decreased drinking. AIY-C diverges from CHOICES in its cultural content, its universal approach, and its youthful age range. AIY-C supports all young AIAN women in making current (for sexually active or drinking youth) or future (among abstinent youth) healthy choices about contraception and drinking. AIY-C contains features that make it highly amenable to mHealth approaches, including a framework for integrating diverse cultural teachings, few modules of short duration, and concrete opportunities for goal-setting and achievement. This proposed project is innovative in its plan to recruit AIAN young women from major urban areas in the US through social media and to deliver AIY-C via mobile devices—both of which are increasingly ubiquitous among AIAN young adults.^{28,29} While social media recruitment and mHealth interventions are not new,

including for adult AEP prevention,³⁰⁻³³ only very recently have they been used with AIAN populations.³⁴⁻³⁶ Appropriate partnership with urban AIAN organizations is foundational to the project's success.³⁷ We have engaged strong collaborators to guide us through social media recruitment strategies, mHealth intervention translation and implementation, and evaluation processes in urban AIAN settings. Engaging with cultural and intervention expert guidance, we propose the following specific aims:

- SA1: **Develop social-media-based recruitment strategies** for urban AIAN young women; we will pilot and refine these strategies.

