NWC mobile app. Findings from our IDIs informed the content to include in our mobile app. The app contains six sessions; these sessions include content on alcohol use, birth control and safer sex, and facts of AEP and FASD. The app also includes culturally relevant imagery such as the medicine wheel and connections across generation. Motivational interview elements of tone, assessment of personal risk, decisional balance exercises, and goal setting are also included. Participant knowledge of alcohol and birth control methods, including condoms, is assessed through the app. See Appendix A for a selection of images from the App.

IV. Research Methods

We propose using an RCT with a baseline sample n=700 urban AIAN young women aged 16 to 20 to evaluate NWC for its effectiveness in AEP prevention.

Figure 1. NWC Conceptual Model

Outcome Measure(s): Figure 1 depicts the measures used the assess the impact of NWC. These measures include demographics, such as age, education level, and income, measures of social risk; environmental support; and cultural identity. Theoretical mediators include knowledge of effective contraception and alcohol use during pregnancy and self-efficacy related to sexual activity and contraceptive and alcohol use. Our primary outcomes include sexual activity, abstinence, effective contraceptive

use, and alcohol and other substance consumption—AEP protective and risk factors. With the pandemic, we have also added measures on experiences with COVID-19 to capture appropriate context.

B. Description of Population to be Enrolled:

Our population of focus will be AIAN women, ages 16-20, who live in urban areas (50,000 people or more), and who are not pregnant or breastfeeding at the time of enrollment. Currently, we are awaiting approval from the Southcentral Foundation of Alaska, a research review IRB for Alaska Native healthcare in

Anchorage (the only urban area in Alaska with population > 50,000). Until we receive this approval, we will exclude residents from Alaska.

C. Study Design and Research Methods

Screening

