G. Data Analysis Plan:

All intervention effectiveness analyses will be based on an intention-to-treat approach. For continuous outcomes (frequency/quantity indices of alcohol) and mediational outcomes (alcohol and contraceptive self-efficacy), we will estimate a series of latent growth curve models (LGCM) in Mplus to assess the effect of intervention exposure on the trajectories of those outcomes over the study period. The "normative" trajectory of an outcome is estimated for the comparison group before estimating the same trajectory among those exposed to the intervention. The third step estimates the degree to which the normative growth trajectory is altered by intervention exposure. On the fourth and final step, the interaction between intervention exposure and pre-intervention status on the outcome is tested. This permits an assessment of the differential effectiveness of the intervention as a function of baseline levels of the outcome variable.

For dichotomous outcomes, Latent Markov Models (LMM) will be used to evaluate transitions between behavioral states (e.g., sexually active to abstinent) throughout follow-up. 166,167 Intervention status is modeled as a time-invariant covariate; its effect on the transition probabilities is estimated freely. Effectiveness is indicated if those in the intervention have significantly lower probabilities than the controls of transitioning out of the abstinence state and significantly higher probabilities of transitioning out of the sexually active state. LMM may also reveal that early sexual experience among control group participants predicts sexual activity across the course of the study but that this relationship is interrupted among intervention participants. Other moderators of intervention effectiveness will also be explored (e.g., enculturation).

H. Summarize Knowledge to be Gained:

If successful, the overall study will generate evidence of NWC effectiveness for AEP prevention by demonstrating: 1) increased effective contraceptive use or sexual abstinence among urban AIAN young

women; 2) decreased or eliminated alcohol use in urban AIAN young women who drink; and 3) maintained abstinence (sexual or alcohol) among those who have this as their goal. If successful, the project will also provide vital information about the feasibility of mHealth interventions for reaching urban AIAN young women or other urban AIAN populations who might otherwise not access health information or interventions

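### Section G's only written effectiveness criterion for dichotomous outcomes covers sexual-activity transitions; effective contraceptive use, a primary outcome, has none, and the rule's 'and' can be read two ways

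*Combined protocol and SAP*

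**What the plan says.** Under Outcome Measure(s) in section IV, the protocol states "Our primary outcomes include sexual activity, abstinence, effective contraceptive" use, together with alcohol and other substance consumption. The opening section says the adapted intervention "preserves the brief MI format and focus on AEP prevention through increased contraceptive use and decreased drinking", and that it "supports all young AIAN women in making current (for sexually active or drinking youth) or future (among abstinent youth) healthy choices".

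Section G assigns Latent Markov Models to dichotomous outcomes, with a move from sexually active to abstinent given as an example. It then gives its one decision rule. The first half is "Effectiveness is indicated if those in the intervention have significantly lower probabilities than the controls of transitioning out of the abstinence state". The second half, in the same sentence, is "and significantly higher probabilities of transitioning out of the sexually active state". Contraception appears elsewhere in section G only among the "mediational outcomes (alcohol and contraceptive self-efficacy"), which go to growth-curve models. Section G opens with "All intervention effectiveness analyses will be based on an intention-to-treat approach".

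Item 1 of section H, the summary of knowledge to be gained, is "increased effective contraceptive use or sexual abstinence among urban AIAN young" women.

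The paragraph on intervention and survey progression (section IV.C) times the surveys at 2, 6 and 12 months, counted from programme completion.

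**The concern.** Both halves of the rule count changes in sexual activity. A participant who stays sexually active and starts effective contraception makes neither of the counted moves, although the intervention is built partly to produce that change. If the intervention worked mainly in this way, the written rule would report nothing, and the team could end up choosing a criterion for a primary outcome with the data in view.

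The *and* raises a second question. Read literally, both transitions must be significant. Read loosely, either one is a sign of benefit. The plan does not say what is concluded when only one is significant.

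**Working it through.** **Plan figures.** No number is attached to the rule. The sample size comes without alpha, power or effect size, so it cannot be rederived. Only the attrition arithmetic can be checked: 1 − 525/700 = 25%, and 525/(1 − 0.25) = 700.

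**Inputs from the protocol.** Final N is 525 (SA3). Background figures in the opening section are 50% of AIAN high-school girls having had sex in the last 3 months, and 80% of AIAN youth not using effective contraception at last sex, hence 20% using it. The survey-progression paragraph gives three post-programme surveys. The payment schedule under procedures/modes of data collection implies four (a first post-intervention survey plus 3 follow-ups).

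**Assumed.** Two-sided 0.05 with only favourable results counted; 1:1 allocation, so 525/2 ≈ 262 per arm; control exit per interval of 30% from abstinence and 15% from sexual activity; equal intervals; observed states without measurement error. Three intervals unless stated. Simulations used 10,000 to 20,000 replicates.

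**1. Which moves the rule counts.**
- Abstinent to sexually active: counted (first half).
- Sexually active to abstinent: counted (second half).
- Sexually active, starting or stopping effective contraception: not counted.

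**2. Contraception-only effect under the rule.** With sexual activity unchanged, each test is favourable with probability 0.025. Both: 0.025² = 0.000625. Either: 1 − 0.975² = 0.049. Simulation agrees (about 0.06% and 5%).

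**3. The same effect on a protected/not-protected outcome.** The share sexually active after three intervals is 0.30/0.45 + (0.50 − 0.30/0.45) × 0.55³ = 0.639. Protected = (1 − 0.639) + c × 0.639, where c is the contraception rate among the active:
- c = 20%: 48.9%
- c = 30%: 55.3%
- c = 40%: 61.7%

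A two-proportion test with 262 per arm has power 84% for 48.9% vs 61.7% and 31% for 48.9% vs 55.3%. If the active share stays at 50%, protected is 0.50 + 0.50c: power is 67% for 60% vs 70% and about 22% for 60% vs 65%.

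**4. What the reading of *and* changes when both transitions improve.**

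| Intervals | 30%→25% and 15%→20%: both significant | either/both ratio | 30%→20% and 15%→25%: both significant | either/both ratio |
|---|---|---|---|---|
| 1 | 3% | about 11 | 25% | about 3.1 |
| 2 | 8% | about 6 | 62% | about 1.5 |
| 3 | 16% | about 4 | 85% | about 1.2 |
| 4 | 25% | about 3 | 94% | about 1.06 |

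At three intervals, either suffices in 65% (smaller effects) and 99% (larger effects).

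**5. Abstinence-only effect.** If exit from abstinence falls from 30% to 20% and nothing else changes, that transition test has 87% power. The protected comparison has 34% to 35%.

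**6. Why contraceptive use alone is a poor substitute.** In the larger-effect case of step 4, the active share in the intervention arm is 0.20/0.45 + (0.50 − 0.20/0.45) × 0.55³ = 0.454. If abstinent participants are coded as non-users, use is 0.20 × 0.639 = 12.8% in controls and 0.20 × 0.454 = 9.1% with the intervention. A beneficial shift to abstinence then looks like harm.

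**The case against.** The strongest reply is that section G gives the Latent Markov Model to dichotomous outcomes in general and marks sexual activity as an illustration. The effectiveness sentence continues that illustration, so matching transitions for contraceptive use may be intended, and section H supplies the direction. This stands in part: a reader might infer that contraceptive use will not be analysed at all, and the documents do not support that. The gap is in the criterion. The states, the coding of abstinent participants, the contrast and the decision rule for contraceptive use are not written.

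A reader might also infer that the team must pick a criterion after seeing the data. Nothing prevents it from setting one beforehand; the plan only leaves the later choice open.

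Nor is the *and* shown to be an error. The wording tolerates a looser reading, and the fourfold difference at three intervals is one cell of an assumed grid.

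Extending the transition rule to contraceptive use would be a smaller change than a new composite. The composite follows section H item 1 directly and avoids the coding problem in step 6, but it is a choice with a cost (step 5).

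**Conclusion.** The concern holds as a gap in the stated criterion. It goes beyond missing detail, because the written rule applied to a contraception-only benefit would succeed only at chance level; that follows from the wording and needs no assumed rates.

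The *and* needs clarifying. Its effect is large for modest improvements (about 3- to 11-fold across one to four intervals) and close to none for larger effects with more intervals.

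A reader might take section H to make contraception alone sufficient for trial success. It does not: its three items are joined by *and*, and it is a summary of knowledge to be gained, so contraception or abstinence is one component.

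All powers rest on the assumed transition rates, alpha, 1:1 allocation, equal intervals and observed states. The planned surveys are unequally spaced and the planned model is latent, so these are illustrations and not powers of the planned analysis. The point should be fixed before analysis.

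**What to change.** 1. Before analysis, add to section G a criterion matching section H item 1: protected (abstinent or using effective contraception) versus not protected. Compare arms as randomised at the 12-month survey, using a repeated-measures logistic model (arm by wave) adjusted for baseline state. State which answers count as effective contraception and as abstinent, the recall period, and how abstinent participants are coded. Say that this covers the sexual/contraceptive outcome only; alcohol keeps its growth-curve analysis.
2. Keep the Latent Markov Model. Report each transition with its own estimate and confidence interval, and state whether both must be significant.
3. As a separate point, surveys are triggered by completion of a self-paced programme, so a non-completer has no defined follow-up survey. Give non-completers a schedule that does not depend on completion, set the same way in both arms, so that the intention-to-treat analysis can include them. Completers' schedule need not change; section I describes the trial as ongoing, and moving everyone's clock is more than is needed.

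Cost: plan wording, one extra standard model, and some extra surveys for non-completers. Sexual activity and contraceptive use are already listed outcomes, but the survey instrument is not in the documents, so whether its items give the needed recall period has to be checked. The protected outcome is less sensitive to an abstinence-only effect (about 35% against 87% under the assumed rates), and the programme also serves abstinent young women, so the transition results must still be reported.
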